The time taken to place the block will be recorded from the time the ultrasound probe is first placed on the child until completion of local anesthetic injection. The observer collecting postoperative data will not be present when the block is placed, and a band-aid will be placed over the supraclavicular fossa in all patients to maintain blinding of the observer to the group assignment. During the operation patients can receive intraoperative fentanyl, 1 mcg/kg IV at a time, if the attending anesthesiologist believes it is clinically indicated. At the end of the operation, anesthetic gases will be discontinued while the patient breathes 100% oxygen. The trachea will be extubated when the patient responds to commands, and the child will then be taken to the Post Anesthetic Care Unit (PACU) in keeping with standard practices. A validated pain scale (verbal rating scale where 0 = no pain and 10 = worst possible pain ever) will be used throughout to assess the severity of pain in the postoperative period. In keeping with current practice, patients with pain scores >4 will be treated with morphine 0.05mg/kg IV at 10 minute intervals until the score is below 4. Oral acetaminophen with hydrocodone (Lortab elixir 0.15mg/kg hydrocodone) will be administered to children for pain scores between 2-3. Supplemental oxygen, rescue antiemetic and antipruritic drugs will be administered in keeping with standard practices of TCH and the clinical judgment of the Attending Anesthesiologist. The duration of supplemental oxygen therapy, any medication administered and complications (side effects such as nausea, vomiting, itching, respiratory depression, prolonged awakening) will be recorded on the case report form.

The blinded observer will record pain scores within 15 minutes of arrival in the PACU and at 30 minutes, 1,2,6,12,24, and 48 hours after arrival in the PACU. If the child is sleeping at this time, the scores will be recorded when awake. The observer will also document any additional medication, the dose and the time given.

Prior to discharge home, parents will be educated on use of the 0-10 pain scale and given a diary to keep an accurate record of postoperative pain issues through the study period. The goal is to capture maximum pain scores at rest and with movement. Patient and parental satisfaction with pain management and with the global perioperative experience will also be graded on a numeric scale 0-10 scale.

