## Section G: Sample Size/Data Analysis

### G1. Sample Size

How many subjects (or specimens, or charts) will be used in this study?

Local: 188 Worldwide: 188

Please indicate why you chose the sample size proposed:

In a retrospective IRB approved study, the peak pain scores in the PACU were  $2.8 \pm 2.9$  in the group receiving systemic analgesia without a regional block. A group size of 34 would have an 80% power of detecting a clinically relevant difference in the peak pain scores of 2 at the 0.05 level of significance, assuming the same SD in pain scores in the treatment group. We will recruit 40 patients in each group to allow for dropouts and incomplete data. This group size would

have a 90% power of detecting a 75% increase in time to first analgesia in the regional anesthesia group compared to the IV analgesia group, based on the retrospective study.

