## G2. Data Analysis

Provide a description of your plan for data analysis. State the types of comparisons you plan (e.g. comparison of means, comparison of proportions, regressions, analysis of variance). Which is the PRIMARY comparison/analysis? How will the analyses proposed relate to the primary purposes of your study?

The primary endpoint of the study will be the peak or maximum pain score in the postoperative period. The secondary endpoints in the study will include (1) Opioid consumption in morphine equivalents (2) Time to first analgesia request (3) Time to achieving discharge readiness (4) Incidence of side effects such as vomiting, respiratory depression, itching, dysphoria, compartment syndrome (5) Patient and parental satisfaction. In order to keep the statistical analysis robust, we will also examine the differences in subjects who did or did not return the diaries regarding: a. group assignments b. age c. gender d. ASA physical status e. duration of surgery f. intraoperative opioids medications g. time of the PACU stay h. mean and peak pain scores and i. recorded opioid consumption in the PACU before discharge. These are known factors k that affect postoperative pain and failure to show a difference in these factors may suggest that the missing 48 hour data can be considered to be missing at random. We will also examine the PACU pain and opioid consumption data(first 2 hr after surgery) for all cases and separately for cases where the diaries were returned with the 48 hour data. If the conclusions regarding the secondary endpoints of pain in the PACU were not altered and the known factors affecting postoperative pain did not differ between those who did and did not return the diaries, it may suggest the conclusions are still robust. Our current plan will be modified to include not only daily phone calls from researchers, but Epic Mychart as well for protected email communication to better gather data.

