Descriptive statistics will be used for each group. The peak and mean pain scores, age, weight, opioid consumption, time to first analgesia and discharge readiness and satisfaction scores will be compared between the two groups using Students t test if the data is normally distributed, and nonparametric tests if the data are skewed. A Fisher's exact test or a Chi Square test with Yates correction will be used to compare the number of patients in each group with side effects as listed above. P values of <0.05 will be considered to be statistically significant.

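### Time to first analgesia, a secondary endpoint, can be right-censored, but the plan tests it with methods that need a time for every child and gives no rule for children with no dose or lost before one

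*Combined protocol and SAP*

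**What the plan says.** Section G2 lists "Time to first analgesia request" among the secondary endpoints. Its analysis paragraph puts the endpoint in one list with pain scores, weight and age: "opioid consumption, time to first analgesia and discharge readiness and satisfaction scores will be compared between the two groups using Students t test". Skewed data go to nonparametric tests, but none is named. No section mentions censoring or a survival method.

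Section F2 ties PACU analgesics to pain scores: morphine above 4, and an oral opioid that "will be administered to children for pain scores between 2-3". No drug is named for scores of 0 or 1. Section I expects that children given the block may need less medication.

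Pain scoring runs to "48 hours after arrival in the PACU". After discharge, medication data come from a diary and from calls on postoperative days 1 to 3. The observer notes the dose and time of each drug; the diary is described only as a list of medications.

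On missing data, section G2 compares families who did and did not return the diary, including by assigned group. It reasons that finding no difference may suggest that "the missing 48 hour data can be considered to be missing at random".

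Section G1 says of the group size of 40 that it would "have a 90% power of detecting a 75% increase in time to first analgesia", citing a retrospective study. It gives no control time, spread, event share or test.

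**The concern.** A t test or an ordinary rank test needs one number per child. Two kinds of children may have none: those followed to the end without a dose, and those lost before a first dose. The plan's own text makes both plausible. At least three rules fit section G2: drop them, give them the last follow-up time, or censor them. The choice could therefore be made after the data are seen.

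The rules do not give the same answer. Event-free children are the ones the block is meant to produce, so dropping them removes the children who benefit most. Scoring last contact as if it were a dose turns unequal loss into an apparent difference in time.

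Other terms are also open. The event is a request in the endpoint list but simply first analgesia in the analysis and power text. No time origin is given for this endpoint: pain scores and discharge readiness are timed from PACU arrival, the diary from surgery. Follow-up could end at 48 hours or at the day 3 call.

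**Working it through.** **1. The plan's own figures.** The sample size for the primary endpoint reproduces: a difference of 2, SD 2.9, 80% power and two-sided 0.05 give 34 per group. The 90% for time to first analgesia cannot be reproduced, because its inputs are not given. What it would require can be worked out:

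- t test, 40 per arm, difference 0.75 × control mean: 90% power needs a standardised difference of 0.734, so the SD can be at most 0.75 / 0.734 = 1.02 times the control mean.
- Log-rank with exponential times, hazard ratio 1/1.75: events = 4 × (1.960 + 1.282)² / (ln 1.75)² = 134.2, so 135. With 80 children all having an event, power is 71%.
- Log-rank with Weibull times, all treated, 40 per arm: simulated power is 89% at shape 1.3 and 95% at shape 1.5.

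So 90% is attainable under some inputs and not under others.

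**2. Bias from dropping event-free children.** Assume exponential times with means of 24 h (control) and 42 h (block), a true ratio of 1.75, and follow-up to L = 48 h. The mean among children with an event is θ − L·e^(−L/θ) / (1 − e^(−L/θ)).

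- Control: e^(−2) = 0.135; 24 − 48 × 0.135 / 0.865 = 16.5 h.
- Block: e^(−1.143) = 0.319; 42 − 48 × 0.319 / 0.681 = 19.5 h.
- Ratio: 19.5 / 16.5 = 1.18 instead of 1.75.

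With L = 72 h the ratio is 1.29. This is a deliberately late first dose; with early dosing the bias shrinks.

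**3. Power under each rule.** Simulation, 3,000 trials per setting, two-sided 0.05, 40 per arm unless stated. Every time and share is an assumption. In all rows but the last, treated children have exponential times with the means shown, and the stated share is never treated. Figures are % power.

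| Setting (control v block) | Dropped, rank | Kept at 48 h, rank | Kept at 48 h, t | Log-rank |
|---|---|---|---|---|
| 2 v 3.5 h; 10% v 30% never treated | 46.6 | 83.4 | 73.7 | 85.4 |
| Same, 94 per arm | 81.5 | 99.5 | 97.7 | 99.6 |
| 2 v 3.5 h; 10% v 20% | 50.8 | 65.0 | 35.6 | 61.1 |
| 2 v 3.5 h; 5% v 10% | 52.6 | 58.6 | 27.6 | 57.9 |
| 2 v 3.5 h; 10% v 10% | 51.3 | 41.1 | 8.1 | 27.9 |
| 2 v 2 h; 10% v 30% | 5.9 | 33.2 | 63.1 | 52.1 |
| 2 v 3.5 h; all treated | 56.2 | 56.2 | 64.9 | 66.5 |
| 24 v 42 h, exponential, cut at 48 h | 14.2 | 53.6 | 54.9 | 60.2 |

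If 20% of each arm is also lost at 2 h in the first setting, power is 39.9% with dropping and 83.1% with log-rank.

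**4. False positives from scoring last contact as an event.** With no true difference (mean 6 h in both arms) and 10% v 30% lost at 2 h, the error rate is 12.5% by rank test and 10.1% by t test, against 5.6% by log-rank. With an equal 20% lost, the rates are 5.1%, 5.0% and 5.1%.

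**The case against.** The strongest reply is that the large losses come from rules the plan does not state. Nothing says that event-free children will be dropped or that last contact counts as a dose. A rank test that keeps event-free children at a common cut-off is valid: its error rate was 5.1% and 4.5% in two checks with no true difference. It is also close to log-rank in the table, and better at 10% v 20% and at 10% v 10%. An unnamed nonparametric test does not even exclude log-rank. All this stands. It means the plan leaves room for a sound analysis, but it does not commit to one, and a common cut-off cannot place a child lost early.

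The diary-return comparison is a real mitigation. It could reveal unequal loss, and the calls and MyChart messages should reduce loss. It is not a censoring rule, and a fully followed child who never needed a drug is not missing data.

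Event-free children are shown to be possible, not common. A PACU score of 0 or 1 does not imply no drug at home over the following days.

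Two stronger readings are tempting. A reader might infer that the 90% power is wrong. The documents do not support that: the inputs lie in a retrospective study not reproduced here, and the 71% ceiling holds only for exponential times. The mismatch between "We will recruit 40 patients in each group to allow for dropouts and incomplete data" and "Local: 188 Worldwide: 188" is a separate sample-size matter. A reader might also infer that the main hypothesis is undermined, since it speaks of longer analgesia. Section D measures that by pain scores, and the primary endpoint is peak pain.

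**Conclusion.** The concern holds as a gap in the analysis of one secondary endpoint. The endpoint can be right-censored, the named methods need a time for every child, and no rule covers children without one. That rests on the text alone and is firm.

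The size is not known. In the 40-per-arm settings with 2 v 3.5 h, dropping costs from about 39 points of power against log-rank (10% v 30% never treated) to 5 points (5% v 10%). With everyone treated, dropping changes nothing. With equal shares never treated, dropping has the higher power, so the argument for log-rank is valid handling of censoring under a rule fixed in advance, not uniformly greater power. The false-positive result needs both unequal early loss and last contact scored as an event. If nearly all children are dosed early and followed, the effect is negligible.

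The 90% power should be described only as stated without its inputs.

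**What to change.** In section G2, take time to first analgesia out of the t test and rank test list. Analyse it by Kaplan-Meier and log-rank, censoring at a stated end of follow-up (48 hours or the day 3 call) or at last contact if earlier. State one event, request or administration, and one time origin. Report event-free and lost children by arm, and use the diary-return comparison to judge whether loss looks related to group or to early pain. Give a hazard ratio only with a check of proportional hazards, since a block that wears off may not meet it; otherwise give medians or restricted mean times. Confirm that the diary or calls record the clock time of the first home dose. In section G1, add the inputs and test behind the 90%.

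The cost is SAP wording and a small data-capture check. Log-rank also has somewhat less power in some settings than a test that keeps event-free children at the cut-off: 61.1% v 65.0% by rank at 10% v 20% never treated, 27.9% v 41.1% by rank at 10% in both arms, and 52.1% v 63.1% by t test when only the never-treated share differs. Log-rank also assumes that loss is unrelated to need for analgesia, which the by-arm report would help readers judge.

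### Does leaving the choice between a t test and a rank test for peak pain score to the observed data undermine the primary analysis?

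*Combined protocol and SAP*

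**What the plan says.** The G2 form asks "Which is the PRIMARY comparison/analysis". The reply names an endpoint: "The primary endpoint of the study will be the peak or maximum pain score in the postoperative period". The method comes later in G2, in a single sentence that covers peak and mean pain scores, age, weight, opioid consumption, times and satisfaction. These are compared "using Students t test if the data is normally distributed, and nonparametric tests if the data are skewed". G2 also promises descriptive statistics by group and sets the threshold: "P values of <0.05 will be considered to be statistically significant".

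G1 takes a PACU peak score of 2.8 ± 2.9 from a retrospective study. It states that 34 per group gives "80% power of detecting a clinically relevant difference in the peak pain scores of 2", "assuming the same SD in pain scores in the treatment group", and then plans 40 per group. The count field in the same section reads "Local: 188 Worldwide: 188", which is 94 per arm at 1:1. That mismatch is a separate matter, so results below are given for both sizes where available. The scale in F2 is a "verbal rating scale where 0 = no pain and 10 = worst possible pain ever".

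**The concern.** The data choose the test, and two careful analysts could choose differently because normality has no definition. The scores may well not be normal: a normal curve with mean 2.8 and SD 2.9 puts 17% of its area below zero on a scale that starts at zero.

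If the rank test is used, its p-value does not speak directly to the 2 points in G1. With a true mean difference of 2 and PACU-type scores, the Hodges-Lehmann shift averages only 1.3 to 1.4 at 34 to 40 per arm. At stake would be a significance verdict that depends on an unstated decision made after the data are seen, and a result that is hard to read against the plan's own clinically relevant difference.

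**Working it through.** **1. The plan's own figure.** Inputs from G1: difference 2, SD 2.9, 0.05, 80% power; two-sided is assumed because G1 does not say.

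n = 2 × [2.9 × (1.960 + 0.842) / 2]² = 33.0 per arm by the normal approximation, which rounds up to 34. The noncentral-t solution is 33.99, with power of 80.0% at 34, 86.1% at 40 and 99.7% at 94. A one-sided calculation gives 26, so G1 was computed as a two-sided comparison of means.

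**2. Would the rank test need more patients?** For a shift in location, divide by the relative efficiency: 33.0 / 0.955 = 34.6 (35 per arm) if scores are normal, and 33.0 / 0.864 = 38.2 (39 per arm) in the worst case. Both fit within 40, although 39 uses nearly all of the dropout allowance.

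**3. Behaviour of the rule.** Beta-binomial scores on 0-10 were simulated, with 4,000 trials per scenario at 40 per arm. The distributions are assumed, since the documents give only 2.8 ± 2.9. Two ways of reading the rule were tried: t test only if Shapiro-Wilk p > 0.05 in each arm, or only if |skewness| < 1 in each arm. Entries are the percentage of trials with p < 0.05. The last column is the percentage in which the t and rank tests disagree.

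| Control v block | t | Rank | Shapiro rule | Skewness rule | Disagree |
|---|---|---|---|---|---|
| 2.8 ± 2.9 v same (null) | 5.2 | 4.8 | 4.8 | 5.2 | 3.1 |
| 2.8 ± 2.9 v 0.8 ± 1.5 | 97.5 | 96.3 | 96.3 | 96.4 | 2.5 |
| 2.8 ± 2.9 v 0.8 ± 2.0 | 94.4 | 99.3 | 99.3 | 99.3 | 5.0 |
| 4.8 ± 2.9 v 2.8 ± 2.9 | 85.5 | 88.6 | 88.6 | 85.8 | 3.5 |
| 2.8 ± 2.9 v 1.8 ± 2.5 | 36.3 | 41.4 | 41.4 | 41.4 | 11.2 |

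The criterion does decide the branch. In the 4.8 v 2.8 row the skewness rule sends 72% of trials to the t test and Shapiro-Wilk sends almost none. Power still differs by only 88.6 − 85.8 = 2.8 points. At 94 per arm, the tests disagree in 0.3% of trials or fewer when the true difference is 2 points.

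**4. Type I error.** Across 34, 40 and 94 per arm the two rules gave 4.7% to 5.2%. A separate run with rounded-beta scores gave the skewness rule 5.4% to 5.8%. If someone ignored the rule and always took the smaller p-value, the range over all null scenarios was 5.3% to 7.7%.

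**5. What fixing one test would buy.** Power of the mean-based test against the rank test, rounded-beta scores, control 2.8 ± 2.9:

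| Block arm | n per arm | Mean-based | Rank | Mean minus rank |
|---|---|---|---|---|
| 1.8 ± 2.9 | 40 | 34% | 61% | −27 |
| 1.8 ± 2.9 | 94 | 65% | 93% | −28 |
| 0.8 ± 2.5 | 40 | 88% | 99.9% | about −12 |
| 1.3 ± 2.3 | 40 | 72% | 85% | −13 |
| 1.8 ± 2.3 | 40 | 39% | 35% | +4 |
| 1.8 ± 2.3 | 94 | 74% | 68% | +6 |

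In the PACU-type scenarios with a real effect, the skewness rule sends at most 12% of trials to the t test at 40 per arm. The plan's rule therefore keeps most of the rank test's advantage where that advantage is large.

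**6. Unequal SDs.** At a block mean of 0.8 the SD cannot exceed √(0.8 × 9.2) = 2.71, so 2.9 in both arms is impossible on the PACU values. With 1:1 allocation this does no harm: Welch and Student power agree within 0.2 points in every scenario run, and a smaller block SD makes G1 conservative.

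**The case for a change.** The best case for a change is that the form asks for the primary comparison and gets only an endpoint, that two sentences would settle it without new data, and that the verdict can turn on the branch. With a true difference below 2 points, the tests disagree in 10% to 16% of trials at 34 to 40 per arm for PACU-type scores, and in 24% to 28% if the block arm is 1.8 ± 2.9. A bare p-value also cannot show whether 2 points was reached. With SD 2.9 the 95% half-width is 1.29 points at 40 per arm, so the interval matters.

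The text is indeed silent on all of this, and naming a test and an interval would be tidier. The consequences are smaller than they look. With two independent arms and one score per child, the ordinary nonparametric choice is the Wilcoxon-Mann-Whitney test. The promised group summaries, if given as mean and SD like the source data in G1, yield the difference and its interval directly: 1.991 × 2.9 × √(2/40) = 1.29. The largest disagreement figures arise mainly because the mean-based test misses what the rank test detects, so they do not argue for fixing the mean. The 2 points in G1 is a sizing assumption, and the plan does not make it a threshold for success.

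**Conclusion.** The concern does not call for a change. G2 leaves the test and the between-group estimate unspecified, but following it as written does not bias the comparison, holds type I error at 4.7% to 5.8%, and costs at most 3 points of power between reasonable normality criteria at a true 2-point difference. Misuse by picking the smaller p-value is bounded at about 7.7% in the scenarios run.

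Which single test to fix is a fair trade-off: a mean-based analysis matches the scale of G1 but can lose 27 to 28 points of power under strong skew, while in other cases it gains 4 to 6. Reporting the mean difference with its interval beside whichever test is used is ordinary analyst practice and needs no amendment.

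These conclusions rest on assumed score distributions. The plan gives only the PACU mean and SD, and the primary endpoint covers the whole postoperative period. Monte Carlo error in the 4,000-trial runs is about 0.4 points near 5% and at most 0.8 points elsewhere.

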**F2. Procedure**

Written consent will be obtained by the investigators prior to the surgical procedure using the IRB approved consent form. The medical record will be examined and the use of any analgesic medications in the 24 hours prior to the procedure will be recorded. Patients will be taken to the OR and anesthetized using standard procedures of the Texas Children's Hospital (TCH) department of anesthesia, including monitoring according to the American Society of Anesthesiologists guidelines (EKG, pulse oximetry, BP, temperature and end-tidal expired carbon dioxide and inhalation anesthetic gases). If the Attending Anesthesiologist believes the child is at risk for aspiration of gastric contents, a rapid sequence induction with propofol 3-4 mg/kg and succinylcholine 1mg/kg IV will be performed with cricoid pressure, in keeping with standard practices. In other patients an IV will be started after induction of anesthesia. An age appropriate endotracheal tube or appropriate sized LMA will be inserted in all patients. Anesthesia will be maintained with sevoflurane, nitrous oxide and oxygen, adjusted to keep blood pressure and heart rate within 20% of baseline values, in keeping with standard practices. All patients will receive ketorolac 0.5mg/kg IV.

Patients will be randomized in a 1:1 ratio into one of two study groups: ultrasound guided supraclavicular block or IV opioids, based on a computer generated random number by using Random Allocation Software For Parallel Group Randomized Trials. The assignment will be made only after written informed consent has been obtained. There will be an equal chance a child will be assigned to one of the two groups. Patients randomized to the systemic analgesia group will receive 1mcg/kg of fentanyl IV after induction. Patients randomized to the supraclavicular block group will receive an ultrasound guided nerve block with 0.2 ml/kg ropivacaine 0.5% (maximum 10 ml), using the technique described by Marhofer et al. In order to decrease variance in success rates, the ultrasound guided nerve block will be performed by the Regional Anesthesia team. The Regional Anesthesia team has become well established at Texas Children's Hospital and all members of the team have successfully performed >100 ultrasound guided supraclavicular blocks in the past. Supraclavicular blocks were performed using the higher frequency of the probe and placing it in a coronal-oblique-plane in

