## Section H: Potential Risks/Discomforts

### H1. Potential Risks/Discomforts

Describe and assess any potential risks/discomforts; (physical, psychological, social, legal, or other) and assess the likelihood and seriousness of such risks:

All patients in this study will undergo general anesthesia. Risks of general anesthesia consist of airway issues like sore throat, laryngospasm, pulmonary aspiration and hypoxia. Postoperative nausea and vomiting can also occur in up to 40% of children. Serious side effects of general anesthesia can include heart rhythm disturbances, stroke, brain damage, and even death (1 in 200,000). These risks are present even if the child does not participate in the study as the procedure requires general anesthesia. The risks of IV pain medications are the same whether they are on this study or not and will be explained separately (since those risks are not specific to the study). The dose of opioids used in the study population is not different from our current standard practice. Therefore, the side effect profile should be no higher than any other patient undergoing a similar procedure at our institution even if they do not participate in the study. The risks of ultrasound guided supraclavicular block include accidental vascular puncture, local anesthetic toxicity, pneumothorax, and permanent nerve injury. In adults undergoing ultrasound guided regional anesthesia, this has been reported to occur in 0.1 -0.3%. There are few large scale studies in children, the landmark article by in 2006 quotes a complication rate of 23 instances out of 24000 regional anesthetics performed with an incidence of 0 for peripheral nerve blocks. Therefore we believe the risk related to receiving regional blockade as very unlikely. A prospective randomized study was performed in adults undergoing arthroscopy with regional anesthesia. The rate of postoperative neurologic symptoms was 0.4% [2]. Again following standard practice protocols, this risk is no higher than any other patient receiving a supraclavicular ultrasound guided regional blockade at Texas Children's Hospital.

We are unaware of any risks from ultrasound which is used routinely in pregnant women for assessment of the fetus. There is also a risk of loss of confidentiality of data despite the steps taken to prevent this as listed in section K.

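### The side-effect tests are valid but conservative; naming Boschloo's exact test would recover some power on this secondary endpoint while still holding the 5% level

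*Combined protocol and SAP*

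**What the plan says.** All references are to the combined protocol and SAP.

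- **G2, Data Analysis.** Side effects are the fourth of five secondary endpoints; the examples listed are vomiting, respiratory depression, itching, dysphoria and compartment syndrome. For these, a Fisher's "exact test or a Chi Square test with Yates correction will be used to compare the number of patients in each group". The criterion is "P values of <0.05 will be considered to be statistically significant". G2 does not say which of the two tests applies when, whether testing is two-sided, or how the several comparisons are handled together. It specifies no effect estimate or interval for them.
- **G1, Sample Size.** The justification is for the primary endpoint only: "A group size of 34 would have an 80% power of detecting a clinically relevant difference in the peak pain scores of 2", then "We will recruit 40 patients in each group to allow for dropouts and incomplete data". The header of the same section gives "Local: 188 Worldwide: 188". No target difference or power is stated for side effects.
- **F2, Procedure.** "Patients will be randomized in a 1:1 ratio into one of two study groups", so a total of 188 would be 94 per group.
- **H1, Potential Risks.** The one usable event rate: "Postoperative nausea and vomiting can also occur in up to 40% of children".
- **Section C, Background.** Compartment syndrome is put at 0.1-0.3%.

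**The concern.** Fisher's test conditions on the total number of events, and the Yates correction is built to imitate it. With small groups and few events, the possible p values are coarse, and the chance of falling below 0.05 under no difference can be well short of 5%. The unused part of the 5% is lost power.

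That matters here because section I names fewer drug side effects as a possible benefit of the block, so this comparison carries part of the trial's rationale. An exact unconditional test guarantees the same 5% ceiling without conditioning on the event total. If one is uniformly at least as powerful, the planned choice gives up power without need.

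**Working it through.** **Inputs.** From the documents: 40 per group (G1 text); 188 in total (G1 header), which at 1:1 (F2) is 188/2 = 94 per group; alpha 0.05 (G2); nausea and vomiting up to 40% (H1). Assumed: two-sided testing, all block-arm rates, and both rates in any pair that does not start from 40%.

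**The plan's own figure.** G1 powers peak pain for a difference of 2 with SD 2.9. By the normal approximation, n = 2(1.960 + 0.842)² × 2.9²/2² = 2 × 7.85 × 8.41/4 = 33.0, rounded up to 34. The t-test calculation gives 33.99, with 80.0% power at 34 per group. The stated 34 reproduces and is unaffected by what follows.

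**Method.** For n per group, take every pair (a, b) of event counts: 41 × 41 = 1681 tables at n = 40. For each test let R(a, b) = 1 if p < 0.05 and 0 otherwise. Then

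- power(p1, p2) = Σ R(a, b) · Bin(a; n, p1) · Bin(b; n, p2);
- size(p) = power(p, p), and maximum size is the largest value over p between 0 and 1.

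Boschloo's p value ranks tables by Fisher's p and takes the largest probability, over the common rate, of a table at least as extreme.

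**True size (%).**

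| Common event rate | n = 40: Fisher | Yates | Boschloo | n = 94: Fisher | Yates | Boschloo |
|---|---|---|---|---|---|---|
| 5% | 0.4 | 0.4 | 1.4 | 2.0 | 1.8 | 3.6 |
| 10% | 1.7 | 1.4 | 3.1 | 2.8 | 2.6 | 4.1 |
| 20% | 2.8 | 2.2 | 4.0 | 3.4 | 3.4 | 4.6 |
| 40% | 3.0 | 3.0 | 4.8 | 3.4 | 3.4 | 4.7 |
| Maximum, any rate | 3.3 | 3.3 | 4.8 | 3.6 | 3.6 | 4.98 |

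**Power (%).**

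| Rates | n = 40: Fisher | Yates | Boschloo | Gain over Fisher | n = 94: Fisher | Boschloo | Gain over Fisher |
|---|---|---|---|---|---|---|---|
| 40% v 20% | 40.8 | 40.5 | 47.6 | 6.8 | 81.9 | 85.6 | 3.7 |
| 40% v 15% | 64.1 | 63.3 | 70.0 | 5.9 | 96.6 | 97.6 | 1.0 |
| 30% v 10% | 53.4 | 49.4 | 59.2 | 5.8 | 92.0 | 93.8 | 1.8 |
| 20% v 5% | 41.1 | 36.9 | 48.4 | 7.3 | 85.6 | 88.8 | 3.2 |
| 10% v 2% | 10.9 | 10.8 | 20.4 | 9.5 | 54.6 | 63.0 | 8.4 |

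**Containment.** At both sizes every table rejected by Fisher or by Yates is also rejected by Boschloo, so it cannot lose power to either.

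**An example.** With 14/40 v 6/40, Fisher gives p = 0.069 and Boschloo p = 0.045.

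**Dropping the correction is not equivalent.** The uncorrected Pearson chi-square reaches a size of 5.9% at 40 per group.

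**The case against.** Several points on the other side stand.

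- **The planned tests are standard and valid.** P<0.05 is a ceiling, and a test with a true size of 3% respects it. A reader might infer that G2 contains a statistical error; it does not.
- **The trial may be larger than 80.** A reader might infer that both tests always run far below 5%. At 94 per group Fisher's size is about 3.4% at event rates of 20-40%, and the gain from Boschloo is 1 to 4 points for the first four pairs above. The larger gain of 8.4 points is at 10% v 2%, where both rates are assumed.
- **Boschloo is also conservative at low rates.** At a 5% rate and 40 per group its size is 1.4% against Fisher's 0.4%: better, but still well under 5%.
- **The recovered alpha is not free.** G2 lists five example side effects and has no multiplicity rule. As an illustration, take five independent comparisons, each at a common 40% rate. The chance of at least one false positive at 40 per group is 1 − (1 − 0.030)⁵ = 14% with Fisher and 1 − (1 − 0.0476)⁵ = 22% with Boschloo. That is on the high side, since not all listed events are that common, but the direction is right.
- **The H1 rate is a loose anchor.** It is an upper figure for nausea and vomiting together, while G2 lists vomiting.

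A reader might also infer that the test choice makes null safety findings falsely reassuring and that Boschloo cures this. For compartment syndrome at 0.1-0.3%, every test has size and power near zero. Only an interval shows what a null result leaves open: with 0/40 in both groups, the Newcombe 95% interval for the risk difference is ± 1.96²/(40 + 1.96²) = ± 3.84/43.84 = ± 8.8 percentage points.

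Last, the open choice between the two tests might be read as room to pick a result. Their decisions differ in only 8 of 1681 tables at 40 per group, so its effect is small, though one test should still be named.

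**Conclusion.** The point holds as a cheap improvement to a secondary analysis. Fisher and Yates keep the error rate below 5% but use at most 3.3% of it at 40 per group and 3.6% at 94. Boschloo keeps the guarantee (4.8% and 4.98%) and is never less powerful than either at these sizes. Over the pairs shown, it adds about 6 to 10 points over Fisher at 40 per group; at 94 per group it adds 1 to 4 points for most pairs and about 8 at 10% v 2%.

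This rests on two-sided testing and on assumed event rates, apart from the 40%. It does not make the trial adequately powered for side effects: at 40 per group, 40% v 20% has under 50% power even with Boschloo. The primary analysis and the 34 per group are untouched.

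**What to change.** In G2, replace the Fisher-or-Yates sentence with: side effects will be compared between groups by Boschloo's exact test, two-sided; the risk difference will be reported with a 95% confidence interval (for example Newcombe's); and the Boschloo p value decides significance if the two disagree.

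The last clause is needed. At 40 per group the Newcombe interval excludes zero in 20 tables where Boschloo is not significant, with a combined probability of up to 5% under 20% v 5%.

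Cost: one sentence, no new data or patients, and a test available in standard software. The downsides are a less familiar test and somewhat more of the 5% spent on each of several comparisons. G2 should therefore also say whether these comparisons are descriptive or adjusted for multiplicity. For very rare events, rely on the interval rather than the p value.
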